### 3.2 Selection of Study Population

Written informed consent, enrollment in the study, or dispensing of study products cannot begin until the Investigator has received Institutional Review Board (IRB)/Ethics Committee (EC) approval to conduct the study.

To reduce the foreseeable factors that could compromise the outcome of the clinical investigation, subjects are targeted who are experienced contact lens wearers. To be eligible to participate, subjects must have physiologically normal anterior segments not exhibiting clinically significant biomicroscopy findings, no active ocular disease or allergic conjunctivitis, not using any topical ocular medications and be willing and able to follow instructions. There are no known or foreseeable factors that may compromise the outcome of this clinical investigation that are not already controlled for by the Inclusion and Exclusion criteria.

Healthy male and female volunteers will be recruited and screened as per criteria outlined below. The subjects will all be experienced soft contact lens wearers in both eyes.

Enrollment will take place throughout the duration of the study.

### **Intended Purpose/Use**

The kalifilcon A Daily Disposable [REDACTED] lenses are intended for the daily wear correction of refractive ametropia (myopia, hyperopia and astigmatism). Daily disposable lenses are to be prescribed for single use, daily disposable wear. The lenses are not intended to be cleaned or disinfected and should be discarded after a single use.

Additional information can be found in IB and in the comparator lens package insert, patient instruction booklet, and professional fitting guide.

### **Investigational and Target Population**

The relationship between the investigative population and the target population is they are both contact lens wearers. Daily disposable toric lenses are for use by patients prescribed the correction of refractive ametropia (myopia, hyperopia and astigmatism), regardless of gender or ethnicity and who do not have contraindications for the device. This study will be conducted on adults of at least 18 years of age.

Recruitment for this study will target experienced soft contact lens wearers that have refractive error requiring contact lens correction. Subjects will be targeted that have a toric contact lens correction.

Additional information can be found in IB.

### **3.2.1 Eligibility**

#### **3.2.1.1 Inclusion Criteria**

To be eligible for entry into the study, the subject must:

1. Be 18 years or older on the date the Informed Consent Form (ICF) is signed and have capacity to read, understand and provide written voluntary informed consent.

2. Have physiologically normal anterior segments not exhibiting clinically significant biomicroscopy findings.
3. Have no active ocular disease or allergic conjunctivitis.
4. Not be using any topical ocular medications.
5. Be willing and able to follow instructions.
6. Have signed a statement of informed consent.

### **3.2.1.2 Exclusion Criteria**

The subject is not eligible to participate in the study if the subject is:

1. Participating in a conflicting study in the opinion of the Investigator.
2. Considered by the Investigator to not be a suitable candidate for participation.

### **3.2.2 Point of Enrollment and Randomization**

The study is randomized. The study investigator and subject will be masked. An unmasked designee will be responsible for dispensing study products to the subjects according to the randomization schedule. The randomization schedule will be produced prior to study enrollment by Bausch + Lomb's unmasked statistician not otherwise involved in the study.

Randomization will be completed by the unmasked designee. The subjects will be assigned randomization numbers sequentially as they are enrolled. The unmasked designee is responsible for preparing the clinical trial materials according to the randomization schedule. The unmasked designee is also responsible for maintaining study lens inventory, randomization schedule and the Product Accountability Log in a masked fashion.

### **3.2.3 Subject Completion**

The subject will have completed the study when he/she has worn all of the study lens types. Subjects who require further follow-up due to an ongoing Adverse Event will be followed according to the Adverse Event Section 6.0.

The Investigator may discontinue a subject during the study for any reason if, in his or her opinion, it is in the best interest of the subject. Reasons for discontinuation include but are not limited to:

- adverse effects
- other ocular complications
- subject non-compliance
- subject request
- subject found to be ineligible during study participation\*

\*Any subject enrolled in the study, who later is found to have not met any of the eligibility criteria at entry, will be discontinued at the Sponsor's request.

Subject discontinuations will be documented clearly on the applicable case report form. Subjects that are discontinued from the study following randomization will not be replaced.

Exit visits should be completed for early terminated subjects.

The completion of the clinical investigation shall be deemed to coincide with the last visit of the last subject and when follow-up is complete.

### **3.2.4 Lost to Follow-up**

Subjects who do not return for scheduled follow-up visits, as defined by the visit window and cannot be contacted, are to be considered lost to follow-up. All attempts to contact the subject should be documented and kept with the subject's source documentation, and the applicable CRF/eCRFs will be completed.

### **3.3 Investigators**

The study will be conducted at one investigative site, the Bausch + Lomb Research Clinic in Rochester, NY by Investigators who are employed by Bausch + Lomb. The Investigators are qualified by training and experience to conduct this study. All the study procedures will be performed by Optometrists who are licensed to fit contact lenses.

The assessments required for the study are routinely performed by Optometrists and are standard of care for contact lens wearers. (See Appendix A: Methods of Clinical Evaluation for detailed information about study procedures).

### **3.4 Study Duration**

The clinical investigation will take approximately 1 month to complete.

### **3.5 Protocol Changes and Amendments**

Changes to the protocol will be approved by the Sponsor. An amendment to the protocol may also require submission and approval from the IRB before implementation. The Investigator is responsible for ensuring that staff involved have completed training on the changes before implementing with subjects.

## **4.0 STUDY MATERIALS**

Bausch + Lomb will provide all study materials. Subjects must use only study supplied contact lenses during the study visits. Use of other prescribed contact lenses and solution is not permitted during the study visits.

### **4.1 Description of the Test Lens:**

**Test Lens:** kalifilcon A Daily Disposable Toric [REDACTED] (T01: kali A toric)

### **4.2 Description of Comparator Lenses**

Comparator Lenses: Commercially available contact lenses

C01: Total1 for Astigmatism (C01: Total1fA)

C02: Precision1 for Astigmatism (C02: Precision1fA)

C03: MyDay Toric (C03: MyDay Toric)

More information on the commercially available study lenses can be found in the package inserts patient instruction booklets and professional fitting guide .

#### **4.3 Instructions for Use and Administration**

Study lenses will be dispensed to subjects meeting all eligibility requirements including any dispensing requirements in this clinical protocol. Subjects will be dispensed an adequate supply of study lenses to complete the study. Lost or damaged study lenses may be replaced at the discretion of the Investigator. An unmasked designee will be responsible for all study lens accountability, including dispensation and collection of study supplies to subjects.

The investigator or designee will instruct all subjects to adhere to the Subject Instructions provided with their study contact lenses.

Subjects will be instructed not to use any other contact lenses or lens care products while wearing the study lenses.

The subjects will be masked to the study lenses. An unmasked designee at each site will be responsible for all study lens accountability, including dispensation and collection of study supplies to subjects.

Subjects will be receiving each of the study lens types once, in a randomized order. The subject will wear a pair of study contact lenses for approximately 10 minutes. See Appendix B for additional Instructions for Use.

##### **4.3.1 Storage Requirements**

All study materials provided by the Sponsor must be stored in a secure location accessible only to unmasked study personnel.

##### **4.3.2 Subject Instructions**

Subject Instructions for the use of study lenses are included in Appendix B, which include precautions and warnings related to contact lens wear. Subjects must comply with the instructions provided to them.

The Investigator or other designee must review, with the subject, the Subject Instructions and the precautions and warnings, as appropriate for the study.

Any subject who does not follow instructions to a degree that, in the Sponsor or Investigator's opinion, jeopardizes the subject's well-being or the validity of the study, should be discontinued.

#### **4.4 Other Study Materials**

Worn and unworn study lenses will be returned after the study is complete. No other study materials will be used in this study.

#### 4.5 Packaging and Labeling

**Test Lens:** kalifilcon A Daily Disposable Toric [REDACTED]

#### **Comparator Lenses: Commercially available contact lenses**

The comparator contact lenses will be packaged with commercial labels.

C01: Total1 for Astigmatism (C01: Total1fA)

C02: Precision1 for Astigmatism (C02: Precision1fA)

C03: MyDay Toric (C03: MyDay Toric)

#### 4.6 Accountability

The investigational site is responsible for keeping current and accurate records of the amount of study materials received and dispensed, and its disposition. The study lenses must be stored under the appropriate conditions in a secure area and are to be dispensed only to subjects enrolled in the study, in accordance with the conditions specified in this protocol.

All study materials will be accounted for on the Clinical Trial Materials Form and Lens/Solution Tracking Form. Subjects must return all remaining study materials to the Investigator at the final study visit, or their exit visit if discontinued prior to this visit.

#### 4.7 Masking

The investigators and subjects will be masked to the study lens types. Unmasked study personnel will be responsible for dispensing and collecting study lenses and accountability.

The randomization schedule will be created prior to the start of the study by an unmasked statistician not otherwise involved in the study.

In the event that unmasking of a subject's randomly assigned treatment is required, the Investigator (or designee) will reference the subject specific randomization schedule (or login to the EDC System) and unmask the subject.

Whether unmasking occurs inadvertently or intentionally, the Investigator must record the date, time, and reason for unmasking the study treatment in EDC System.

The contact lenses will be inserted into the subject's eye. The unmasked designee is not to show the study blister packs and foils to the Investigator or the subject. An effort will be made to conceal the study lenses from the subject and Investigator throughout the study.

#### **4.8 Product Replacement**

Not applicable, as subjects will not leave the office with study lenses for this insertion only study.

#### **4.9 Risk Assessment**

Information concerning potential risks associated with the investigational device (as well as possible interactions with concomitant medical treatments and risk-to-benefit ratio) can be found within the Investigator's Brochure. Risks are also summarized within the Informed Consent Form (ICF) document. The assessments required for the study are routinely performed and are standard of care for contact lens wearers. The subjects will be informed of any potential study specific risks in the ICF or if new risks become apparent during the study.

##### **4.9.1 Risk Related to Subject**

With contact lens wear there may be increased risk of corneal edema (swelling of the cornea) which may temporarily affect vision or comfort, neovascularization (small blood vessels growing into the cornea), giant papillary conjunctivitis (small bumps on the inside of the eyelids), iritis (internal inflammation in the eye), corneal infiltrates (corneal inflammation) and corneal erosion/abrasion or corneal infection, which if untreated may cause ocular problems.

The risks involved in this study will be minimized because the subjects will be examined frequently and at specified intervals. The risks are further minimized by the study eligibility criteria.

The subject may not personally benefit from being in this study other than getting the opportunity to wear different types of contact lenses. However, study results may allow a new or improved product to be marketed in the future giving benefit to other contact lens users.

No clinical benefit is expected from this feasibility study.

##### **4.9.2 Risk Related to Data Management**

[REDACTED]

[REDACTED]

#### **4.10 Relevance of Clinical Investigation**

Further information regarding the relevance of this study in the context of state-of-the-art clinical practice such as background information, summary of relevant literature, mechanism of action, intended clinical performance, and a summary of existing relevant clinical data of the investigational device can be found in the Investigator's Brochure.

### **5.0 STUDY METHODS**

The clinical procedures in this study are part of normal eye examination. There are not any deviations from normal clinical practice. The procedures conducted in the study are outlined below and described in Appendix A: Methods of Clinical Evaluation.

Following identification of a potential subject, the Investigator (or designee) will explain the purpose of the study, procedures, risks/benefits, and subject responsibilities to the potential subject. The subject's willingness and ability to meet the follow-up requirements of the study will be determined. If the subject chooses to participate in the investigation, written informed consent will be obtained. The subject and the person obtaining written consent will sign and date the IRB-approved ICF. The Investigator must keep the signed ICF document. The signed original document should be retained in the subject's records, and a copy should be provided to the subject. In addition, the applicable privacy regulation requirements must be met. Additional Informed Consent information is provided in Section 8.10.

### **5.1 Measurements and Procedures**

#### **5.1.1 Study Visits**

##### **Visit 1:**

### **5.1.2 Unscheduled Visits**

Additional visits may be scheduled, as necessary, to ensure the safety and well-being of subjects. All additional exams should be fully documented on Unscheduled Visit forms as appropriate.

### **5.1.3 Missed Visits**

If a subject misses a Study Visit, the visit is considered missed, and the subject must be exited from the study. The Investigator or designee must check the missed visit box on the first page of the applicable CRF/e-CRF for that visit.

See Section 3.2.4 Lost to Follow-Up for applicable instructions for subjects who do not return for the final visit.

### **5.1.4 Post-Study Follow-up Visit**

There is no planned follow-up period after the clinical investigation is complete. If a subject requires further follow-up upon discontinuation or completion of the study, the Investigator must schedule post-study follow-up visits, as necessary. The Investigator is required to follow the subject until the condition no longer warrants further follow-up for study purposes. A Post-Study Follow-up Visit e-CRF/CRF must be completed for each of these visits.

There will not be any routine eye care provided after the clinical investigation is complete. Subjects should follow-up with their eye care provider every 1-2 years for comprehensive eye care or sooner as recommended by their eye care provider.

## **5.2 Study Completion**

The subject has completed the study when the subject has completed all of the study lens types. Subjects who require further follow-up will be followed according to the Adverse Event or Post- Study Follow-Up Section. There is no planned follow-up period after the clinical investigation is complete.

The completion of the clinical investigation shall be deemed to coincide with the last visit of the last subject and when follow-up is complete.

### **5.2.1 Study Termination/Suspension**

If during the study it becomes evident that the study should be stopped prematurely or placed on hold, appropriate notification will be given to the requestor and IRB/ECs, as applicable. Should the Investigator and/or study requester wish to terminate the study, the following Research Clinic procedure will be followed. Any subjects with ongoing Adverse Events at the time of premature study termination or hold will be followed by the Investigator.

### **5.2.2 Study Termination Procedure**

The decision to terminate a study will be made by the Director, Vision Care Clinical Research and/or the Principal Investigator (PI). A final slit lamp examination should be performed, and adverse events handled accordingly. In the event that this study is suspended or terminated early, the Investigator (or designee) will reference the subject specific randomization schedule (or login to the EDC System) and unmask the subject.

All investigational materials (lenses, solutions, and / or devices) will be retrieved, all subjects will be exited and the Trial Master File will be reconciled. A clinical report will be written and include the reason for study termination.

### **5.3 Concomitant Medications/Therapy**

Ocular, systemic or topical medications that, in the Investigator's opinion, could potentially affect ocular physiology or lens/solution performance are prohibited.

### **5.4 Protocol Deviations**

The date of and reason for deviations will be documented in all cases. Significant or major protocol deviations impacting the safety of the subject or the integrity of the study must be reported by the Investigator to the IRB immediately. Reporting of all other protocol deviations must adhere to the requirements of the governing IRB/EC.

Any subject enrolled in the study who later is found to have not met the eligibility criteria at entry will be discontinued. Otherwise, unless the protocol deviations put the subject at risk or the subject's condition requires that they be discontinued from the study, subjects may continue to participate until the end of the study.

All investigators participating in this study agree to conduct the study in accordance with the relevant, current protocol and agree to only make changes in a protocol after being notified by the Sponsor, except when necessary to protect the safety, rights, or welfare of subjects. Under emergency circumstances investigators may proceed without prior approval of the IRB. These deviations will be documented and reported to the IRB as soon as possible. The sponsor will not grant protocol waivers for this study.

Corrective Action plans will be developed and completed as deemed necessary for Investigators who deviate from this protocol in a way that adversely affects the rights, safety or well-being of the subject(s) and/or the quality or integrity of data. The Corrective Action Plan will outline the deviation and the site's corrective and/or remedial actions.

Decisions regarding critical deviations that merit investigator disqualification and will be documented in the Trial Master File.

## **6.0 ADVERSE EVENTS (AE)**

Subjects who experience an adverse event during study participation will be discontinued from study participation but will be followed by the Investigator until resolution of the adverse event or until the Investigator determines that further improvement is not expected.

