## 7.0 STATISTICAL METHODS

### 7.1 Study Endpoints

The primary endpoint is Primary gaze orientation 5 minutes after lens insertion.

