#### **7.5 Study Populations**

Subjects will be included in all summaries under the treatment that they actually received. Analyses of safety data will include all dispensed subjects. All other summaries will include all eligible, completed subjects.

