##### **7.6.3 Exploratory/Sensitivity Analysis**

There are no planned exploratory or sensitivity analyses for this study.

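### The completers-only rule in section 7.5 discards valid 5-minute orientation readings from any subject who stops before wearing all four lenses, and the stop may be related to a lens

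*Combined protocol and SAP*

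**What the plan says.** The primary endpoint (section 7.1) is a short-interval reading: "The primary endpoint is Primary gaze orientation 5 minutes after lens insertion". The Synopsis and section 4.3 give about 10 minutes of wear per pair. Each subject receives the four lens types once, in random order.

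Section 7.5 keeps all dispensed subjects for safety. For everything else it states: "All other summaries will include all eligible, completed subjects". It also states: "Subjects will be included in all summaries under the treatment that they actually received".

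Section 3.2.3 defines the completer: "The subject will have completed the study when he/she has worn all of the study lens types". Section 5.2 gives a second definition that uses *completed* where 3.2.3 uses *worn*. Section 3.2.3 adds: "Subjects that are discontinued from the study following randomization will not be replaced". Section 7.6.3 adds: "There are no planned exploratory or sensitivity analyses for this study".

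Two sections deal with stopping after an adverse event. Section 6.0: "Subjects who experience an adverse event during study participation will be discontinued from study participation". Section 3.2.3: "The Investigator may discontinue a subject during the study for any reason if, in his or her opinion, it is in the best interest". An open list of reasons comes next, and adverse effects head it.

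**The concern.** The study compares lenses within subjects, and each lens yields its primary reading halfway through its own wear period. When a subject stops early, the readings on the earlier lenses are already complete. If the stop comes in the second half of a wear period, so is the reading on the current lens. Section 7.5 removes all of them from the primary summary because the subject did not go on to wear the remaining lenses.

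Two things are at stake. The first is loss of valid primary-endpoint data. About 30 subjects are enrolled against a target of 30 completing each lens type (section 3.1), with no replacement, so there is little or no margin. The second is selection. A subject may stop because of how a lens behaved, so the completers are chosen partly on an event that may depend on a lens. No planned analysis would show the effect.

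**Working it through.** **No figure to reproduce.** Sections 7.2 and 7.3 are redacted, and the visible plan gives no adverse event rate. The check is a count of readings, followed by a calculation over assumed rates.

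**Inputs from the documents.** 30 subjects (3.1); 4 lens types (Synopsis); reading at 5 minutes (7.1); about 10 minutes of wear per pair (Synopsis, 4.3). Planned lens-pair readings: 30 × 4 = 120. Planned wear: 30 × 4 × 10 / 60 = 20 subject-hours.

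**Step 1: readings discarded per stopped subject.** Under 7.5 a non-completer keeps 0 of 4.

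| Stop occurs on | Taken and discarded, stop before 5 min | Taken and discarded, stop after 5 min |
|---|---|---|
| Lens 1 | 0 | 1 |
| Lens 2 | 1 | 2 |
| Lens 3 | 2 | 3 |
| Lens 4 | 0 if *worn* governs; 3 if *completed* governs and the stop breaks completion | 0 or 4, likewise |

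**Step 2: expected number of subjects lost.** Let p be the assumed chance of an event per lens wear, q = 1 − p, and let every event end participation.

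- Under *worn* (3.2.3), only events on lenses 1 to 3 cost a completer: expected loss = 30 − 30q³; chance of losing at least one = 1 − q⁹⁰.
- Under *completed* (5.2), if a lens-4 stop also counts: expected loss = 30 − 30q⁴; chance of at least one = 1 − q¹²⁰.

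| p (assumed) | Lost, *worn* | At least one | Lost, *completed* | At least one |
|---|---|---|---|---|
| 0.5% | 0.4 | 36% | 0.6 | 45% |
| 1% | 0.9 | 60% | 1.2 | 70% |
| 2% | 1.8 | 84% | 2.3 | 91% |
| 3% | 2.6 | 94% | 3.4 | 97% |

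**Step 3: readings recovered by using all those taken (under *worn*).**

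- Events after the reading: 30(1 + q + q² + q³) − 120q³ = 0.9, 1.8, 3.5 and 5.2 of 120 at the four rates.
- Events before the reading: 30(q + q² + q³ + q⁴) − 30(3q³ + q⁴) = 0.4, 0.9, 1.7 and 2.6.

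**Step 4: precision.** Losing k of 30 widens a confidence interval by the factor √(30/(30 − k)). For k = 1, 2 and 3 that is 1.7%, 3.5% and 5.4%.

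**Step 5: how often a paired difference can be restored.** After s readings in random order, the chance that the test lens and a given comparator have both been read is C(s,2)/C(4,2): 0 for s = 1, 1/6 for s = 2, 1/2 for s = 3. If stops are spread evenly over lenses 1 to 3, the average is (0 + 1/6 + 1/2)/3 = 22% when the stop follows the reading, and (0 + 0 + 1/6)/3 = 6% when it precedes it.

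**The case against.** The completer set is stated openly, in a feasibility study with no pass/fail criteria, and it summarises every lens on the same subjects. Using all readings gives up that balance. This is a genuine cost, but keeping the completer summary as supportive meets it.

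The expected loss is small. In 20 subject-hours of wear, at the 0.5% rate and under *worn*, the likeliest result (64%) is that no completer is lost. That stands, and it limits the weight of the point.

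A reader might infer that sections 6.0 and 3.2.3 contradict each other outright. The documents do not support that. The list in 3.2.3 already includes a mandatory reason, since its footnote requires ineligible subjects to be discontinued. Section 6.0 can be read as the specific rule, and always discontinuing would satisfy both. Section 6.4 and the visit procedures are not visible and might settle the matter. What remains is unclear drafting, and it affects only how many subjects stop. The loss of readings comes from 7.5 under either reading.

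A reader might also infer that every early stop costs readings. A stop on lens 1 before 5 minutes costs none.

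Finally, a reader might expect the change to undo a bias of some size. If one of 30 subjects is dropped whose between-lens difference lies an assumed 10, 20 or 30 degrees from the average of the others, the comparison moves by 10/30 = 0.33, 20/30 = 0.67 or 30/30 = 1.0 degree. That is not a measure of what the change recovers. The difference can be restored only if both lenses had been read, which step 5 puts at 22% or 6% of evenly spread stops.

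**Conclusion.** The point holds as a fault in the analysis set. Current, unredacted text discards one to three valid primary-endpoint lens-pair readings from a subject stopped on lens 2 or 3, or on lens 1 after 5 minutes. The position for lens 4 is unclear because 3.2.3 and 5.2 define completion differently.

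The exclusion cannot be assumed random. Its direction is unknown and its size is probably small: 0.4 to 2.6 of 30 subjects, or 0.6 to 3.4 under the 5.2 wording. Those figures rest on assumed event rates of 0.5% to 3% per wear and on every event ending participation. The discarded readings remain in the database, and safety summaries are unaffected.

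This does not threaten the study. It is worth changing because it concerns the primary endpoint and the remedy is a wording edit. The drafting of 6.0 and 3.2.3 is a secondary point.

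**What to change.** 1. In 7.5, state that each valid 5-minute primary gaze orientation reading from an eligible subject is summarised under the lens worn, whether or not all four lenses were worn. This fits the existing rule of summarising by treatment received.
2. Make paired comparisons with a method that accepts incomplete sets, for example a mixed model with subject as a random effect.
3. Keep the completer summary as supportive.
4. Use one definition of completion in 3.2.3 and 5.2, so that a stop during lens 4 has a single answer.
5. Reconcile 6.0 with 3.2.3 on whether an adverse event ends participation, and check the Appendix B instruction about removing a lens and inserting a new one (Adverse Reactions) against the result. Which rule applies is for the sponsor to decide; items 1 to 3 work under either.

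Cost: wording only, with no extra subjects, visits or measurements. The downside is that numbers per lens may differ by a few subjects and some pairs will be incomplete. The change preserves readings already taken. It cannot supply those never taken, so it reduces the selection without removing it.
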